Study protocol: «Comparative assessment of the efficacy and safety of venoactive drug treatment of pelvic venous disorders: results of a single-center randomized open trial»

ID: NCT06584799

Date: 09/04/2024

Project Summary

Venoactive drug (VAD) therapy is one of the most effective methods of treating chronic venous diseases (CVD) [1-3]. Numerous studies have proven its high efficacy in relieving symptoms of CVD, such as leg pain and swelling, leg heaviness and fatigue, as well as an association between the VAD intake and acceleration of venous ulcer healing [4-8]. Pelvic venous disorders (PeVDs) represent a group of pathological conditions including varicose veins of the pelvis and vulva, and compression stenoses of the left renal and common iliac veins. Although PeVDs are associated with venous lesions of the pelvis and retroperitoneum and have specific clinical manifestations, they are one of the forms of CVD and constitute a separate cohort [9,10]. A number of studies on the VAD usage in PeVD indicate the wide possibilities of this type of treatment in eliminating chronic pelvic pain (CPP), the most dramatic symptom of PeVD, which is the main cause of disability and decreased quality of life, social and daily activity in women with PeVD. The healthcare systems of industrialized countries are known to spend annually more than 2 billion US dollars on the treatment of patients with PeVD and CPP, and the cost of treating one patient with PeVD ranges from 3,600 to 27,000 US dollars per year [11-13].

Currently, a variety of VADs are presented on the pharmaceutical market, which, according to the product labels, provide effects not only on the venous outflow from the lower extremities, but also on venous hemodynamics in the pelvis [14]. At the same time, a literature analysis shows that micronized purified flavonoid fraction (MPFF, Detralex, Daflon) has the greatest evidence base obtained in the efficacy and safety studies of VADs in PeVD [15-19]. Nevertheless, patients are rarely interested in the scientific dossier of drugs, and in the real practice the patients with PeVD and CPP most often ask: “What is the best drug to use for the CPP relief?” This is quite understandable, as it is CPP in PeVD that results not only in disability, but also in family conflicts, psycho-emotional stress and depressive states [20,21]. In this regard, patients seek to get rid of pain as soon as possible and strive to use the most effective drug.

Micronized purified flavonoid fraction (MPFF) is a venotonic agent that also has angioprotective properties. It reduces venous distensibility and blood stasis, capillary permeability, and increases capillary resistance. The results of clinical studies confirm the pharmacological activity of drugs containing this active substance in relation to the parameters of venous hemodynamics. MPFF improves venous tone: a reduction in venous emptying time has been shown by venous occlusion plethysmography. In patients with signs of severe microcirculatory disorders the treatment with drugs containing this active substance is associated with a statistically significant (as compared to placebo) improvement in the capillary resistance, as has been shown by angiostereometry. The drug also has a proven efficacy in the treatment of CVD of the lower extremities (Source: https://www.vidal.ru/drugs/detralext_38634; accessed: September 4, 2023).

MPFF 1000 dosing regimen is 1000 mg once daily for 2 months.

2. **Diosmin 600.** Manufacturer: INNOTHERA CHOUZY (France). Active substance: diosmin.

Venotonic action: the drug reduces venous distensibility, increases venous tone, reduces blood stasis, and enhances the vasoconstrictor effect of epinephrine and norepinephrine. The optimal daily dose of diosmin for obtaining venotonic effect is 600 mg.

Angioprotective action: the drug improves microcirculation, increases capillary resistance, and reduces capillary permeability. Effect on the lymphatic system: the drug improves lymphatic drainage, increases the tone and frequency of contraction of lymphatic capillaries, increases their functional density, and reduces lymphatic pressure. It has an anti-edematous effect, reduces symptoms of inflammation (dose-dependent effect), reduces adhesion of leukocytes to the venous wall and their migration into paravasal tissues, and improves oxygen diffusion and perfusion in tissues. The drug hinders the production of free radicals and synthesis of prostaglandins and thromboxane. A double-blind, placebo-controlled study using Duplex ultrasound has confirmed that the drug reduces the mean venous pressure in the system of superficial and deep veins of the lower extremities (Source: https://www.vidal.ru/drugs/phlebodia_600_4622; accessed: September 4, 2023).

Diosmin 600 dosing regimen is 600 mg once daily for 2 months.

3. **Hesperidin + Diosmin 1000.** Manufacturer: ALLIUM (Russia). Active substance: diosmin and hesperidin.

A venotonic agent that also has angioprotective properties. It reduces venous distensibility and blood stasis, reduces capillary permeability and increases their resistance. The results of clinical studies confirm the pharmacological activity of drugs containing this active substance in relation to the parameters of venous hemodynamics. It increases venous tone: a reduction in the time of venous emptying has been demonstrated in studies with venous occlusion plethysmography. In patients with signs of severe microcirculatory disorders the treatment with drugs containing this active substance is associated with a statistically significant (as compared to placebo) improvement in the capillary resistance, which has been proven by angiostereometry. The drug has a proven efficacy in the treatment of CVD of the lower extremities (Source: <https://www.vidal.ru/drugs/gesperidin-diosmin>; accessed: September 4, 2023).

Hesperidin + Diosmin 1000 dosing regimen is 1000 mg once daily for 2 months.

All three of these drugs are venotonic and venoprotective drugs used in the CVD treatment. They are comparable in their pharmacological properties, product labels, profile of side effects and adverse events, and the cost per package of 30 tablets, according to the Moscow chain of

pharmacies (Source: <https://gorzdrav.org/p/detralks-tabl-p-o-1000mg-n30-62440/>; <https://gorzdrav.org/p/flebodia-600-tabl-p-o-600mg-n30-17602/>; <https://gorzdrav.org/p/venarus-tabl-p-o-900mg-100mg-n30-64844/>; accessed: September 4, 2023).

Patients will take these VADs at the same time every morning, during breakfast. Patients will be warned in advance about possible side effects and adverse events. In a case of their occurrence, the patients shall immediately notify the principal investigator or investigators using one or more mobile phone numbers provided to them in advance.

General information

Study title: «Comparative assessment of the efficacy and safety of venoactive drug treatment of pelvic venous disorder: results of a single-center prospective randomized trial»

Protocol ID: NCT06584799.

Protocol of the study: The study was approved by the local ethical committee of the Pirogov Russian National Research Medical University (Protocol No. 20452024)

Responsible for the study: [name], Doctor of Medical Sciences, Professor, Pirogov Russian National Research Medical University, [name]; [contact].

Department: University Surgical Clinic named after V.S. Savelyev, [name].

Rationale

Pelvic varicose veins with blood reflux, described as “Pelvic varicose disease” (PVD) or “Pelvic venous insufficiency” (PVI), represent one of the nosological entities of PeVD [1]. PVD and PVI develop in about 15% of women of reproductive age and 30% of female patients seeking medical help for CPP [2,3]. Two third of patients with PVI have no indications for surgical or endovascular interventions and require only medical treatment, which is based on VAD. The purpose of VAD treatment is to relieve PVI symptoms, primarily CPP, improve venous outflow from the pelvic organs, and reduce venous stasis in the pelvis [4,5]. A variety of diosmin-containing VADs are successfully used nowadays in the treatment of CVD, including PVI. Many studies have proven that their use is associated with the reduction or relief of leg pain, heaviness and swelling, as well as a faster healing of the venous ulcers [6,7]. Moreover, a number of studies have demonstrated a high efficacy of MPFF in relieving PVI symptoms and pelvic pain [8-12]. CPP significantly reduces the quality of life of patients with PVI, their social and household activity, and it is quite natural that patients seek to get rid of this suffering as soon as possible, using the most effective

drug in this regard. One of the most frequently asked questions by patients with PVI is: “What venoactive drug is best to take in order to relief or alleviate CPP?”

6. To evaluate the patients' adherence to the recommended treatment with VADs using MPFF 1000, Diosmin 600 and Hesperidin + Diosmin 1000 in female patients with PeVD.

Study design

This will be a single-center randomized study. The period of the study will be from 2023 to 2024. The study will include 150 female patients with symptomatic PeVD.

Inclusion criteria:

- Age from 18 to 45 years;
- The presence of PeVD symptoms (CPP, dyspareunia, discomfort in the hypogastrium, dysuria, vulvar varicose veins);
- The presence of pelvic varicose veins with reflux in them, according to DUS;
- Pelvic venous reflux (PVR) lasting for greater than 1 s, according to DUS;
- Isolated dilation and reflux in the parametrial and uterine veins, according to DUS;
- Absence of competing abnormalities, accompanied by CPP.

Exclusion criteria:

- Asymptomatic form of the disease;
- Menopause;
- Pregnancy;
- Post-thrombotic disease;
- Neoplasms;
- Competing diseases with CPP;
- Known hypersensitivity to any of the components of the used VAD.

Each patient will sign a voluntary informed consent prior to the inclusion in the study.

Methodology

The study will include 150 consecutive female patients with symptomatic PeVD, according to the inclusion/exclusion criteria. All patients will undergo a clinical examination, transabdominal and transvaginal DUS of the pelvic veins to verify the diagnosis and to determine the diameters of the pelvic veins and the duration of reflux in them. The study will include patients with PeVD and isolated dilation and reflux in the parametrial and uterine veins. Previous studies have shown that the use of VADs in patients with a combination of reflux in the ovarian, parametrial and uterine veins is ineffective [4,14]. The CPP intensity will be assessed using a visual analogue scale (VAS), which is a 10-cm horizontal line ranged from 0 to 10 scores (1 cm equals 1 score). The CPP intensity will be assessed by VAS scores as following: 0, no pain; 1-3, mild pain; 4-6, moderate pain; 7-10, severe pain. After a brief instruction by an investigator, the patients will rate their pain intensity by making a mark on the line.

For randomization procedure, the sealed envelope principle will be used. Three groups of 50 patients each will be formed depending on the recommended VAD usage: group 1 (n=50) with MPFF1000; group 2 (n=50) with Diosmin 600; and group 3 (n=50) with Hesperidin + Diosmin 1000. After the start of VAD intake, the patients will be self-rating the pain intensity on VAS on the weekly basis. After 60 days from the VAD treatment start, the patients will undergo repeated clinical examination and provide an investigator with 8 completed VAS forms. Based on the repeated examination data and the VAS results, a comparative analysis of the clinical efficacy of VADs will be carried out. In a case of side effect or adverse event occurrence during a 2-month treatment course, patients inform the doctor-investigator about it within one day, and the decision is made either to continue, change the regimen of treatment or to discontinue it. Flow chart of the study is presented in *Figure 1*.

[figure not shown]

Figure 1. Flow chart of the study. *Abbreviations:* PeVD, pelvic venous disease; DUS, duplex ultrasound scanning; OV, ovarian vein; PV, parametrial vein; UV, uterine vein; CPP, chronic pelvic pain.

1. *Clinical examination* includes obtaining medical history and information about complaints, physical examination, assessment of the local vascular status and measurement of the pain intensity by VAS. The clinical examination is carried out before DUS of the pelvic veins and then is repeated after completion of the VAD treatment course (i.e. after 2 months).
2. *Transabdominal and transvaginal DUS of the pelvic veins* is carried out after clinical examination and includes assessment of the patency and diameters of the pelvic veins, iliac

veins, inferior vena cava and renal veins, as well as identification of the blood reflux through the pelvic veins (gonadal, parametrial, uterine veins). Separately, the status of the left renal vein (LRV) is evaluated based on the measurements of its diameter and blood flow velocities in the area of intersection with the superior mesenteric artery and in the region of the renal hilum, as well as by calculating the diameter ratios and velocity ratios to assess the degree of LRV stenosis.

3. *Venoactive drug treatment*. Diosmin-containing VADs (MPFF 1000, Diosmin 600, Hesperidin + Diosmin 1000) will be used in accordance with the treatment regimens stated above.

In addition to publishing the results of the study in scientific journals, making presentations at scientific forums and conferences, it is planned to use the results of this study when developing guidelines of the Ministry of Health and posting information about the study results on social networks. The leading role in publications belongs to [name]. The publications will include names of [name], [name] and [name].

Duration of the study

The duration of the project is determined by achieving the required (150 patients) number of participants. The period of a patient's participation in the study, that includes clinical examinations, DUS, and the VAD treatment course, is 2 months. Investigators will be examining the patients before and 2 months after the VAD treatment course.

Expected issues

The issues with patient recruitment are expected, as the female patients with CPP are most often seen and treated by gynecologists. To solve this problem, information letters will be sent to antenatal clinics and outpatient facilities, and interaction will be established with gynecological hospitals. No financial issues are expected, as the study is carried out as part of the University's research program and does not imply any additional funding.

Responsibilities of investigators

Principal investigator [name]:

Recruitment of patients, carrying out DUS, randomization of patients, prescription of treatment to the patients, and control of the patients' eligibility for the study, according to the selection criteria, the completion of documentation, and compliance with ethical standards.

[name], investigator:

Carrying out DUS of the pelvic veins, completion of documentation, and statistical analysis of the data.

[name], investigator:

Recruitment of patients, prescription of treatment to the patients, completion of documentation, repeated clinical examinations of the patients, and statistical analysis of the data.

[name], investigator:

Recruitment of patients, prescription of treatment to the patients, completion of documentation, repeated clinical examinations of the patients, and statistical analysis of the data.

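### In this open trial, the only two investigators listed for repeat examinations also prescribe the drugs and analyse the data; the existing team could separate these roles

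*Protocol*

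**What the plan says.** The title announces "results of a single-center randomized open trial". The protocol describes no masking of patient, examiner or analyst.

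Responsibilities of investigators lists four people:

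- Principal investigator: "Recruitment of patients, carrying out DUS, randomization of patients, prescription of treatment to the patients, and control of the patients' eligibility for the study", plus oversight of documentation and ethical standards.
- Second listed investigator: "Carrying out DUS of the pelvic veins, completion of documentation, and statistical analysis of the data".
- Third and fourth, in identical words: "Recruitment of patients, prescription of treatment to the patients, completion of documentation, repeated clinical examinations of the patients, and statistical analysis of the data".

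Under Methodology, "the patients will be self-rating the pain intensity on VAS on the weekly basis", and each woman hands 8 completed forms to an investigator when she is re-examined after 60 days. The clinical examination covers history and complaints, "physical examination, assessment of the local vascular status and measurement of the pain intensity by VAS". The same section then states: "Based on the repeated examination data and the VAS results, a comparative analysis of the clinical efficacy of VADs will be carried out".

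Data processing and statistical analysis leaves the choice between Student's t test and the Mann-Whitney test to judgement.

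**The concern.** Relief of chronic pelvic pain is the central efficacy objective, and pain is subjective. An examiner who knows the drug, and may have prescribed it, can affect what complaints are recorded, how local vascular status is judged, the setting in which the visit VAS is marked, and how marks on the line are read. If the same person then analyses the data with the arms visible, choices such as which test to use are also made with the allocation known.

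The trial compares three active drugs that the protocol calls comparable in their pharmacological properties. A true difference may therefore be small, and a modest difference in assessment between arms could imitate it. The protocol also plans to use the results when guidelines are developed. A reported advantage for one drug would be easier to defend if prescribing, assessing and analysing had been kept apart.

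**Working it through.** No figure in the plan needs reproducing beyond the arm sizes ("Three groups of 50 patients each will be formed depending on the recommended VAD usage"; 3 × 50 = 150, which agrees). The check sets the role list against the path of the outcome data.

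**Step 1. Roles, from Responsibilities of investigators**

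| Investigator | Randomises | Prescribes | Re-examines | Analyses |
|---|---|---|---|---|
| Principal | yes | yes | no | no |
| Second | no | no | no | yes |
| Third | no | yes | yes | yes |
| Fourth | no | yes | yes | yes |

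Three of four prescribe, two of four re-examine and three of four analyse. Both re-examiners are also prescribers and analysts. One analyst, the second investigator, has neither of the other two duties.

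**Step 2. Outcome data, from Methodology**

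- Weekly VAS: marked by the woman, and complete before the day-60 visit. The examiner can affect only how the forms are received and read.
- Visit VAS: marked by the woman during an examination conducted by the examiner.
- Complaints and local vascular status: recorded or judged by the examiner.

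All of these enter the comparison between drugs.

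**Step 3. What follows**

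The third and fourth investigators each may prescribe for a woman, re-examine her and analyse her data. Nothing in the text prevents this and nothing requires it. The principal investigator prescribes too, and no sentence links a re-examiner to the women for whom that person prescribed.

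**Step 4. Can the present staff be split?**

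Yes. A woman prescribed for by the third investigator can be re-examined by the fourth, and the reverse. A woman prescribed for by the principal investigator can be re-examined by either. The second investigator can analyse.

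**Step 5. Sensitivity to a shift (illustration only)**

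The protocol gives no SD and no size of bias. Assume 50 women per arm, a two-sided 0.05 normal test on one pair of arms, no true difference, and a shift of b SD in one arm on a measure that the examiner can affect. The standard error in SD units is √(2/50) = 0.2, and the false-positive rate is 1 − Φ(1.96 − b/0.2) + Φ(−1.96 − b/0.2).

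| Assumed b (SD) | False-positive rate |
|---|---|
| 0 | 5.0% |
| 0.1 | 7.9% |
| 0.2 | 17.0% |
| 0.3 | 32.3% |

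For b = 0.2: 1 − Φ(0.96) + Φ(−2.96) = 17.0%. This shows how the test reacts to a shift if there is one. It is no evidence that a shift exists or how large it is. Enrolling more women would not remove such a shift.

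**The case against.** The strongest reply is that the trial is openly unmasked. Staff who know the arm are then a declared design choice and not a contradiction, and the main pain record is self-rated on forms completed before the examiner sees the woman. Much of this stands. The greater exposure is probably the unblinded patient rating her own pain, and no change of staff duties touches it.

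Four stronger readings are tempting, and the document does not support them:

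- A reader might infer that investigators choose each woman's drug. Allocation is by sealed envelope, and randomisation is listed only for the principal investigator.
- A reader might infer that every woman is re-examined by her own prescriber. The role list permits this but does not state it.
- A reader might infer that this team favours MPFF, because the Rationale mentions an impression of manufacturer bias. That remark concerns the authors of earlier studies. Nothing says that these examiners favour one drug.
- A reader might count the absence of arm-coded analysis as an omission. It may stand in a statistical analysis plan that is not shown.

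It is also fair to say that examiner masking would be incomplete. Women report side effects by telephone to the investigators, all four roles involve documentation, and adherence and adverse events must still be collected.

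What survives is that the protocol itself assigns these duties to persons, so the overlap is not a detail left to another document, and it can be avoided with the people already named.

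**Conclusion.** The point holds as a recommended improvement, not as an error or contradiction. Both investigators listed for repeat examinations also prescribe and analyse, and the protocol uses the repeat examination for the comparison between drugs. The overlap is certain at the level of listed duties. How often a woman would be re-examined by her own prescriber is unknown.

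The exposure is limited to examiner-recorded findings, the visit VAS, the reading of the forms and analytic choices. The size and direction of any bias cannot be derived from the document. The conclusion assumes that the role list is complete and is followed as written.

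**What to change.** Amend Responsibilities of investigators and the day-60 procedure in Methodology:

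1. Each woman is re-examined at day 60 by an investigator who did not prescribe for her and, as far as possible, does not know her arm. Adherence and adverse events are recorded after the efficacy assessment. The treatment record is kept apart from the examination record.
2. The 8 weekly forms are handed in and the visit VAS is marked before any talk of treatment.
3. The second listed investigator runs the between-drug comparison on data with arms coded A/B/C. Another team member, such as the principal investigator, prepares the coded file. If an analysis plan already provides for this, the protocol need only align the roles with it.
4. The protocol states as a limitation that women know their drug and rate their own pain, which these steps do not change.

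Cost: protocol wording, a scheduling constraint on the day-60 visits and a small data-coding step, with no extra staff. Masking will be partial, because side-effect calls, shared documentation or the women themselves may reveal the arm.
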